7.1.1 Procedures for Discontinuation of Study Treatment

Participants are free to discontinue IP or withdraw from the study at any time without prejudice to further treatment. Discontinuing study treatment is not the same as study withdrawal. Procedures to follow for study withdrawal are detailed below. If the participant decides to withdraw consent, then the reason for this must be recorded separately in the eCRF. A participant that decides to discontinue IP should always be asked about the reason(s) and the presence of any adverse events. The reason for discontinuing treatment and the date of last IP administration should be recorded in the eCRF. Participants permanently discontinuing IP administration should be given locally available standard of care therapy, at the discretion of the Investigator. However, treatment with marketed or investigational biologics is not allowed until Week 76 (for the first 200 participants approximately) or Week 64 (last 200 participants randomised) even if the participant has discontinued IP. Interaction studies between tezepelumab and other biologics indicated for the treatment of asthma have not been

conducted. For additional information regarding pharmacokinetic and pharmacodynamic effects of tezepelumab reference should be made to the Investigator Brochure.

All participants who prematurely discontinue IP should return to the site and complete the procedures described for the premature IP Discontinuation visit (IPD) at 4 weeks (+/-5 days) post last IP administration, except in case of IP discontinuation due to NP surgery.

In case of IP discontinuation due to NP surgery, the IPD procedures (including CT scan if at least 12 weeks passed since the baseline CT scan) must be performed prior to the surgery. Sites are encouraged to schedule the IPD visit (in case of NP surgery) prior to, and as close as possible to the planned surgery date.

Participants who discontinue treatment should be encouraged to return for all regularly scheduled visits for safety and efficacy assessments. In case of IP discontinuation due to NP surgery, no further nasal endoscopies or CT scans are required after the IPD visit.

At the IPD visit the participant will be given 3 options as to how they will be followed as follows:

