- 1 The participant should be encouraged to return for all regular clinic visits and perform all scheduled assessments (excluding IP administration and, in the case of IP discontinuation due to NP surgery, nasal endoscopy and CT) until the EOT visit at Week 52 (+/-5 days).
- 2 The participant will be offered follow-up on a monthly basis via telephone calls while continuing ePRO data collection on the handheld device at home until the participant completes the EOT visit at Week 52 (+/-5 days). The UPSIT assessments will not be completed as per SoA at home after IPD visit until the participant returns to site at the EOT visit.
- 3 If the participant cannot or does not wish to comply with any of the options above, (or any component of them such as only telephone-based visits without completion of the eDiary), the Investigator will contact the participant at 52 weeks post-randomisation. No other study assessments will be performed prior to this contact.

The EOT visit will be completed immediately in the case of subsequent early withdrawal from option 1 or 2. Participants who do not wish to have any follow-up contacts will be discontinued from the study. All discontinued participants must return the eDiary at the EOT visit.

If the participant chooses option 1, all assessments will be completed as per the SoA as indicated in [Table 1](#). If the participant chooses option 2 or 3, the key information to be collected during the telephone calls are AEs/SAEs, changes in concomitant medication, health

care utilisation, and asthma exacerbation information (asthma/AERD/NSAID-ERD participants). Participants who initially choose options 1 or 2 and subsequently cannot or do not wish to comply with the requirements of their option can continue with a less intensive option (ie, participant initially choosing option 1 can continue with options 2 or 3, participants initially choosing option 2 can continue with option 3). Participant Withdrawal from the Study

A participant may withdraw from the study at any time at his/her own request or may be withdrawn at any time at the discretion of the investigator for safety, behavioural, compliance, or administrative reasons. This is expected to be uncommon.

A participant who considers withdrawing from the study must be informed by the Investigator about modified follow-up options (eg, telephone contact, a contact with a relative or treating physician, or information from medical records).

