### 3.1.4 Visit Windows

All summaries and analyses, both efficacy and safety, which are presented by time point (e.g. “Week 52”) will use a visit window to classify the data record, which is derived from the assessment date relative to the reference start date. This approach allows appropriate classification of visits which may have occurred significantly earlier or later than the protocol assessment schedule, as well as the use of data captured at visits which have no fixed timing (notably the IPD visit), and the handling of data captured at visits for which the database label is incorrect and unresolvable.

Nominal database visit numbers will not be used in any summary or analysis by visit.

For Screening/run-in period, the relative day is defined as (Date of assessment – Date of randomization).

For periods after randomization:

For efficacy variables, the reference start date is the date of randomisation, and relative day is therefore defined as (Date of assessment – Date of randomisation) + 1.

For safety variables, the reference start date is the date of first dose of IP, and relative day is therefore defined as (Date of assessment – Date of first dose of IP) + 1.

Any data collected at unscheduled or repeat visits will be listed and will be included in baseline definitions (see Section 3.1.1), and in any definitions of maximum value, minimum value or last value within the relevant study period.

Data collected at unscheduled or repeat visits will also be included in visit windows, and therefore may be included in summaries or analyses by visit or used in any sensitivity analyses which involve imputation of data from participants with non-missing values to participants with missing values. In the case of a missing value at a scheduled visit, which is then followed by a non-missing value at an unscheduled or repeat assessment within the same visit window, the non-missing value at the unscheduled/repeat assessment will replace the missing value at the scheduled visit.

If a participant has more than one non-missing value within the same visit window, the following rules will apply:

- The non-missing value closest to the target day will be selected for analysis at that visit.
- If two non-missing values are equidistant from the target day, the earlier of the two values will be selected for the analysis at that visit.

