#### 4.2.6 Co-Primary Endpoints

##### 4.2.6.1 Primary Estimand Analysis

For the primary estimand the primary analysis of the co-primary efficacy endpoints (mean change from baseline in NPS at 52 weeks and mean change from baseline in NCS at 52 weeks) uses a composite variable strategy in which data collected after nasal polyp surgery will be replaced with the worst possible score (WPS). Data collected after SCS for NP will be replaced with the worst post-baseline observation prior to the SCS for NP (WOCF). Data collected after treatment discontinuation without surgery or SCS for NP will be included in the analysis. For participants whose post-baseline data are all missing, the baseline value will be used in the place of WOCF. For participants who discontinue the study without NP surgery or SCS/biologic for NP, a multiple imputation (MI) approach will be used to impute missing Week 52 value assuming missing at random (MAR). A random seed of 539612 will be used for both monotone and non-monotone imputations.

Of note, biologics are prohibited medications per the CSP Section 6.4. However, if biologics are used for NP, the same strategy used for the SCS for NP will be applied.

The following steps will be taken to generate completed datasets up to Week 52 for analysis:

**Step 1:** Data collected after date of surgery, SCS for NP, or biologic for NP treatment will be set to missing for the purpose of imputation. For the NCS, if the intercurrent event occurred prior to the last day of a bi-weekly interval, the bi-weekly mean NCS for that period and all periods afterwards will be set to missing.

**Step 2:** Based on the dataset from Step 1, the intermittent missing data will be imputed using the MCMC method in SAS PROC MI with an IMPUTE=MONOTONE statement for each treatment group separately. The imputation model will include baseline co-morbid asthma/AERD/NSAID-ERD status, prior surgery status, region, baseline value, and data at each timepoint. 100 imputed datasets will be generated.

**Step 3:** The remaining monotone missing data will be imputed using the MI procedure with the ‘MONOTONE REG’ option for each treatment group separately. The imputation model will include baseline co-morbid asthma/AERD/NSAID-ERD status, prior surgery status, region, baseline value, and data at each timepoint.

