### **4.2.11    Pharmacokinetics and Immunogenicity**

#### **4.2.11.1    Analysis of Pharmacokinetics**

All analyses of PK variables will be based on the PK analysis set as defined in Section 2.1.3.

Serum tezepelumab concentrations will be summarised over time for the on-study period using descriptive statistics (for the tezepelumab group only).

Serum samples for PK are scheduled to be collected at Weeks 0, 4, 12 24, 36, 52, 64 and at the premature IP discontinuation visit, where appropriate. Data will be assigned to weeks based on the windows defined in Section 3.1.4.

The following criteria will also apply for data to be included in the summary table:

- Only pre-dose samples at Week 0.

- Only pre-dose samples at Weeks 4, 12, 24, and 36 and samples at Week 52 that were also between  $\geq 21$  and  $\leq 35$  days post the previous dose.
- All samples for Week 64 that were taken within the visit window defined in [Section 3.1.4](#).

For descriptive statistics of tezepelumab concentrations:

- If, at a given time point, 50% or less of the concentrations are non-quantifiable (NQ), the geometric mean, coefficient of variation (CV), arithmetic mean and SD will be calculated by substituting the lower limit of quantification (LLOQ) divided by 2 for values which are NQ.
- If more than 50%, but not all, of the concentrations are NQ, the geometric mean, CV, arithmetic mean and SD will be reported as not calculable
- If all the concentrations are NQ, the geometric mean and arithmetic mean will be reported as NQ and the CV and SD as not calculable
- The median, minimum and maximum will also be reported

The LLOQ of tezepelumab in serum will be 0.010  $\mu\text{g}/\text{mL}$ .

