#### 4.2.11.3 Exposure-Response Analysis

Tezepelumab participants will be grouped according to drug concentration quartiles. The treatment groups referred to in the following analyses will be the drug concentration quartiles and placebo. Each drug concentration quartile will be compared against the overall placebo group. The same methods described in the primary analyses for the co-primary endpoints in Section 4.2.6.1 will be used.

The four, mutually exclusive, drug concentration quartiles will be derived using the median trough steady state drug concentration data. The median trough steady state is calculated as the median of the observed drug concentration data at weeks 24, 36 and 52 for each individual participant.

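### The exposure-response quartiles in SAP 4.2.11.3 are labelled steady-state trough but count washout samples, so the lowest quartile can mix low exposure with early stopping of study drug

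*SAP*

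**What the plan says.** SAP 4.2.11.3 splits tezepelumab participants into quartiles of a steady-state trough concentration, compares each quartile with all placebo participants, and applies the co-primary methods of 4.2.6.1. The per-participant value is "calculated as the median of the observed drug concentration data at weeks 24, 36 and 52 for each individual participant".

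The only time-since-dose rule is in SAP 4.2.11.1. It is introduced by "The following criteria will also apply for data to be included in the summary table" and reads "Only pre-dose samples at Weeks 4, 12, 24, and 36 and samples at Week 52 that were also between" 21 and 35 days after the previous dose. Section 4.2.11.3 does not refer to it.

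Sampling can continue off drug:

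- SAP 4.2.11.1 schedules PK samples at fixed weeks "and at the premature IP discontinuation visit, where appropriate".
- Protocol 7.1.1 places the "premature IP Discontinuation visit (IPD) at 4 weeks (+/-5 days) post last IP administration", except when the reason is NP surgery. SAP 3.1.4 assigns such visits to week windows by date.
- Protocol 7.1.1 also says: "If the participant chooses option 1, all assessments will be completed as per the SoA as indicated in" Table 1. Option 2 brings the participant back on site at Week 52. Option 3 has no further assessments before a contact at Week 52.

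On outcomes, SAP 4.2.6.1 states "Data collected after treatment discontinuation without surgery or SCS for NP will be included in the analysis", and it sets post-surgery NPS to the worst possible score, which is 8.

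**The concern.** A sample taken months after the last dose is neither a trough nor at steady state. If it counts, low concentration and poor outcome can share one cause, namely stopping study drug. The lowest quartile would then combine people with low exposure on treatment and people who stopped. A worse result there could be taken as evidence that outcome depends on steady-state exposure, although the grouping cannot separate the two. At stake is how this exploratory analysis is read. It carries no alpha.

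**Working it through.** **The plan's own figures.** The SAP states no size or power for this analysis. The effects and SDs used below are those of SAP 1.3, which claims at least 95% power at 2-sided 1% with 200 per arm. NPS: 1.8 / (2.25 × √(2/200)) = 8.0. NCS: 0.87 / (1.22 × √(2/200)) = 7.1. Against a critical value of 2.58, each gives power above 0.9999, which agrees with the claim.

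**Step 1: the metric after stopping.** Protocol 8.3.12.2 equates 16 weeks with 5 half-lives, so the half-life is 3.2 weeks (22.4 days). With 4-weekly dosing, the concentration at week w is the sum of 2^(−(w−d)/3.2) over doses given at weeks d before w, divided by its steady-state value. Example, last dose Week 24: Week 24 (pre-dose) 0.99; Week 36 about 2^(−8/3.2) = 0.18; Week 52 about 2^(−24/3.2) = 0.006. The median is 0.18.

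| Last dose | Median, all three samples | Weeks 24 and 52 only |
|---|---|---|
| Week 16 | 0.03 | 0.21 |
| Week 20 | 0.07 | 0.50 |
| Week 24 | 0.18 | 0.50 |
| Week 28 | 0.42 | 0.50 |
| Week 32 | 0.99 | 0.51 |
| Week 44 | 0.99 | 0.71 |

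Earlier last doses give 0.01 or less with all three samples. Under option 2 (IPD sample plus Week 52) the median is about 0.50 for last doses at Weeks 20-28, 0.001 or less up to Week 16, and 0.99 for Weeks 32-44. Under option 3 it is 0.99 from Week 20 on, with no sample for earlier stoppers, so nobody is misplaced.

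**Step 2: effect on the quartiles.** Simulation of 200 tezepelumab participants. Assumed, because the documents do not give them: between-participant CV 40%, within-participant CV 20%, last dose uniform over Weeks 4-44, benefit lost linearly over 16 weeks starting 4 weeks after the last dose, and no relation between on-treatment concentration and outcome. Lowest-minus-highest quartile gap in NPS with full attendance:

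| Stopping | All benefit lost | Half lost | None lost |
|---|---|---|---|
| 5% | 0.23 | 0.12 | 0 |
| 10% | 0.47 | 0.23 | 0 |
| 20% | about 0.9 | about 0.45 | 0 |

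The NCS gap with all benefit lost is 0.11 and 0.23 at 5% and 10% stopping. If no stopper gives off-drug samples, the gap is 0.

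Attendance matters. With CV 30%, last doses over Weeks 0-44 and all benefit lost, the NPS gap at 10% stopping is 0.13, 0.25 and 0.50 for 25%, 50% and 100% attendance. At 100% attendance, stoppers make up 30% of the lowest quartile, and its mean effect is −1.26 against −1.76 in the highest.

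**Step 3: surgery alone.** From the planning rates in SAP 1.3 (placebo 11%, HR 0.33), 1 − 0.89^0.33 = 3.8% of the tezepelumab arm. This is an upper figure, because a decision need not lead to surgery. With last doses at Weeks 24-48, outcome 8 minus baseline and placebo change 0 (assumed), the gap is 0.15, 0.21 and 0.26 for baseline NPS 7, 6 and 5. It reaches 0.28 at baseline 5 with CV 30%, and falls to 0.07-0.13 if half keep attending.

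**Scale.** SE of a quartile of 50 against 200 placebo: 2.25 × √(1/50 + 1/200) = 0.36. SE between two quartiles: 2.25 × √(2/50) = 0.45.

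**Step 4: with a 21-35-day condition.** The gap is within 0.01 of 0 in every scenario run.

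**The case against.** *The label already implies troughs.* The sentence that defines the calculation adds no filter, and a programmer following it would include washout samples. The PK analysis set does not remove them either. It needs one detectable concentration not affected by factors such as protocol deviations, and stopping study drug is allowed.

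*A median of three is robust.* This holds for last doses at Week 32 or later when the Week 36 sample exists, but not otherwise.

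*Much of the gap is real.* This stands. If benefit fades because the drug has gone, low concentration does go with less effect. A reader might infer that the plan creates a false signal where no exposure-response exists. The documents do not support that in general. It is clearly so only for surgery or other reasons unrelated to drug level, where the poor outcome comes first.

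*The plan compares each quartile with placebo, not lowest with highest.* This also stands. The between-quartile gaps above only illustrate the distortion, and 0.36 is the SE of the planned contrast.

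*Keeping every observed concentration is a defensible choice.* It could be, under another name. It does not measure steady-state trough.

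*The simulation is simplified.* True. Section 4.2.6.1 imputes within treatment group, and 4.2.11.3 makes the quartiles the groups. Imputation within quartiles of about 50 was not modelled.

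**Conclusion.** The point holds as a defect of definition: the rule as written does not produce the quantity it names. Part of any worse result in the lowest quartile would be loss of drug after stopping and part reverse causation. Neither shows a relation with steady-state trough.

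The size can only be given as a range. It is 0 if no benefit is lost or no stopper gives off-drug samples. At the other end, with full attendance and all benefit lost, it exceeds two SEs of the planned contrast at 20% stopping (0.9 against 0.36). Calling the effect simply small, or simply large, goes beyond the documents. The half-life is implied by the protocol; the stopping rate, timing, attendance, loss of benefit and CVs are assumptions.

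A reader might also infer that the co-primary or key secondary results are at risk. They are not, because this analysis is outside the testing hierarchy in SAP 4.1.2. The point is minor and cheap to settle.

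**What to change.** In SAP 4.2.11.3, state that the median uses only Week 24, 36 and 52 samples (including IPD samples assigned to those windows) taken 21-35 days after the previous dose and before any dose given at that visit. Report separately the number and outcomes of tezepelumab participants with no qualifying sample. The IPD clause is needed because no dose follows an IPD sample, so it is not literally pre-dose under 4.2.11.1.

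The cost is a line or two of text and little extra programming, since the filter is close to the one the PK table needs.

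The change has a downside that should be stated with it. With last doses uniform over Weeks 4-44, four of the eleven possible stopping weeks (4, 8, 12 and 16) leave no qualifying sample: 5% × 4/11 = 1.8% of the arm, or 3.6% at 10% stopping. These participants leave the quartiles while placebo stoppers remain. This moves the average quartile-versus-placebo NPS contrast toward tezepelumab by roughly 0.02-0.06 at 5-10% stopping with half to all benefit lost. Later stoppers still qualify and keep their off-drug outcomes, so their attenuation is spread over the quartiles and not removed.

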#### **4.2.12 Biomarkers**

Biomarker values and change from baseline in these values will be summarised descriptively and presented graphically by treatment group up to Week 76:

- FeNO (co-morbid asthma/AERD/NSAID-ERD subset)
- Peripheral blood eosinophils (Cells/ $\mu$ L)
- Total serum IgE (IU/mL)

Analyses for the other exploratory biomarkers will be described in a separate exploratory analysis plan, which will be finalized before the database lock. These results will be reported outside the main CSR, in an addendum, or separately in a scientific report or publication.

#### **4.2.13 Additional Analyses Due to Global/Country Situation Study Disruption**

Efforts are ongoing to collect outstanding data via alternative means where possible when onsite visits cannot be performed due to global/country situation study disruption. All related protocol deviations (important PDs) will be listed and summarised separately for the Randomised analysis set.

#### **4.2.14 Analyses for China and Japan Registration**

To support the registration in China and Japan, selected analyses will be performed for the participants enrolled in the region. The analyses may include but are not limited to disposition, demographic and baseline characteristics, extent of exposure, prior and concomitant medications, efficacy and safety analyses. Details of the analyses may be documented separately. No p-values will be presented. The Cox regression will not be performed for the time to event type endpoints, if there are <10 events across the treatment groups and <2 events in each treatment group.

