This is a Phase 3, multicentre, randomised, double-blind, placebo-controlled, parallel-group, study designed to evaluate the efficacy and safety of tezepelumab 210 mg Q4W administered subcutaneously (SC) using the accessorised pre-filled syringe (APFS) versus placebo in participants with CRSwNP. Approximately, 400 participants will be randomised globally 1:1 to receive tezepelumab 210 mg or matching placebo.

Participants will be stratified by region, prior nasal polyp surgery and co-morbid asthma/AERD/NSAID-ERD. Randomisation will be monitored to ensure that 50%-70% of the study population will have co-morbid asthma/AERD/NSAID-ERD, and at least 50% will have had prior surgery for CRSwNP. When the target percentage of participants in a stratum in a region is reached, consideration will be given to closing the Integrated Web Response System (IWRS) randomisation for that subgroup, which may be done either overall or within a specific region. Once a subgroup is closed, participants in the screening/run-in period in the closed subgroup will not be allowed to be randomised and will be screen failed.

After enrolment, eligible participants will receive a standardised dose of Intranasal Mometasone Furoate Nasal Spray (MFNS) or equivalent INCS and will enter a 5-week screening/run-in period. Equivalent dose should refer to the highest approved country INCS dose for CRSwNP. Participants who meet eligibility criteria will be randomised at Week 0 (Day 0) to receive either placebo or tezepelumab 210 mg SC starting at randomisation (Week 0) and then every 4 weeks thereafter. An end of treatment (EOT) visit will be conducted at Week 52.

There will be two different follow-up periods after the 52-week treatment period. Approximately, the first 200 participants randomised will have a 24-week follow-up (FU) period without any IMP. The remaining participants will have a 12-week FU period without any IMP.

Disclosure Statement: This is a placebo-controlled, parallel-group treatment study with 2 arms that is participant and investigator blinded.

Number of Participants:

Approximately 890 participants are estimated to be screened/enrolled to achieve approximately 400 randomly assigned participants to study intervention.

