Data Presentation	21Aug2024	Clarified imputed date will be capped by Date of Birth when partially missing medical history date is imputed (Section 3.6.8)	N/A	To provide clarification.
Data Presentation	21Aug2024	Clarified presentation on standard of care medications at study entry and disallowed concomitant medications (Section 4.2.4)	Yes CSP v6.0	To provide clarification.
Data Presentation	21Aug2024	Minor update on the categories of cumulative extent of exposure from $>0 - \leq 4$ , $>4 - \leq 8$ , $>8 - \leq 12$ , etc. $>48 - \leq 52$ , and $>52$ weeks to $>0 - < 4$ , $\geq 4 - < 8$ , $\geq 8 - < 12$ , etc. $\geq 48 - < 52$ , and $\geq 52$ weeks (Section 4.2.5)	N/A	For consistency.
Data Presentation	21Aug2024	Clarified the SNOT-22, NPS, NCS responders will be presented on the number and proportion of responders, not non-responders or missing data (Section 4.2.7.2.1, 4.2.8.7, 4.2.9.7)	N/A	To provide clarification.
Data Presentation	21Aug2024	Updated the safety subgroup variable from Race (White, Black or African American, Asian, Other) to Race (White, non-White) (Section 4.2.10.1)	N/A	To keep consistency with efficacy.
Data Presentation	21Aug2024	Removed the locally estimated scatterplot smoothing (LOESS) plot for biomarkers; Removed the conventional unit presentations on blood eosinophils ( $10^9/L$ ) and total serum IgE (mg/L) (Section 4.2.12).	N/A	To streamline analyses.
Data Presentation	21Aug2024	Simplified presentation of disruption due to global/country situation. Corrected the IPD summaries due to global/country situation are performed using Randomised analysis set (Section 4.2.13).	N/A	To streamline analyses and align with corporate TFL standard.
Data Presentation	21Aug2024	Clarified no p-values will be presented for subpopulation analyses performed for the participants enrolled in the region and used in China and Japan registration (Section 4.2.14).	N/A	To provide clarification.
Data Presentation	21Aug2024	Clarified the Cox regression will not be performed for the time to event type endpoints if there are $<10$ events across the treatment groups and $<2$ events in each treatment group in China/Japan subpopulation analyses (Section 4.2.14).	N/A	To provide clarification.

Other	21Aug2024	Fix the formatting issue on inserted reference in SAP v3 (Section 3.2.2)	N/A	Correction.
Other	21Aug2024	Added another reference (Bannick et al., 2024) for robust variance estimation (Section 4.2.7.2.1 and Section 7).	N/A	To provide clarification.

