## 1.2 Study Design

This is a Phase 3, multicenter, randomised, double-blind, placebo-controlled, parallel-group, study to evaluate the efficacy and safety of repeat dosing of tezepelumab 210 mg SC versus placebo in participants with severe chronic rhinosinusitis with nasal polyposis (CRSwNP).

Approximately 400 participants will be randomised globally in a 1:1 ratio to receive tezepelumab 210 mg or matching placebo.

Participants will be stratified by region (China, Japan, and Rest of World [ROW]), prior nasal polyp surgery and co-morbid asthma/AERD/NSAID-ERD. Randomisation will be monitored to ensure that 50%-70% of the study population will have co-morbid asthma/AERD/NSAID-ERD, and at least 50% will have had prior surgery for CRSwNP. When the target percentage of participants in a stratum in a region is reached, consideration will be given to closing the IWRS randomisation for that subgroup, which may be done either overall or within a specific region. Once a subgroup is closed, participants in the screening/run-in period in the closed subgroup will not be allowed to be randomised and will be screen failed.

[figure not shown]
After enrolment, eligible participants will enter a screening/run in period and will have their current inhaled corticosteroid (INCS) therapy standardized to mometasone furoate nasal spray (MFNS) or equivalent INCS at Visit 1 and throughout the screening and study period.

Participants who continue to meet eligibility criteria will be randomised at Visit 3 (Day 0) to receive either placebo or tezepelumab 210 mg SC at randomisation (Week 0) and every 4 weeks thereafter (Weeks 4, 8, 12, 16, 20, 24, 28, 32, 36, 40, 44, 48). A total of 13 doses will be administered. An end of treatment (EOT) Visit will be conducted at Week 52.

The first approximate 200 randomised participants will have a 24-week follow up (FU) period without investigational product (IP) administration to assess durability of benefit. These participants will have the final safety assessment at Week 76. The remaining participants will be followed for 12 weeks after the end of treatment visit, with the final safety assessments at Week 64.

An overview of the study design is provided below in [Figure 1](#).

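### In the China and Japan analyses, the rule for omitting Cox regression makes its own 10-event limit inoperative, so hazard ratios would be fitted on as few as 2 events or with an empty arm

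*SAP*

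**What the plan says.** SAP 4.2.14 plans selected analyses of participants enrolled in China and in Japan to support registration there. It states that "No p-values will be presented" for these analyses. It then sets one restriction, on when a Cox model is left out for time-to-event outcomes: this happens only "if there are <10 events across the treatment groups and <2 events in each treatment group". The August 2024 entry in the SAP's Amendment History uses the same wording and calls it a clarification. Neither document gives another minimum event count for a Cox fit.

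The Protocol synopsis describes a "parallel-group treatment study with 2 arms". SAP 1.2 says "Approximately 400 participants will be randomised globally in a 1:1 ratio" and names China, Japan and Rest of World as the regional strata, but no regional sample size is given. For the study as a whole, SAP 4.2.7.1.4 to 4.2.7.1.6 apply Cox models to three key secondary endpoints: SCS and/or surgery decision, surgery decision alone, and SCS alone. Kaplan-Meier proportions accompany each model.

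**The concern.** The rule has two limits, one on total events and one on events per arm. Joined by 'and', both shortfalls must occur before the model is dropped. With two arms the per-arm shortfall already forces the total to 2 or fewer, so the limit of 10 adds nothing. A limit that can never operate suggests that the sentence does not say what was meant.

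At stake is the quality of the regional hazard ratios. These analyses carry no p-values, so a Cox fit contributes only the hazard ratio and its interval. If one arm has no events, the estimate runs to zero or infinity. With two or three events split between the arms it is finite but nearly uninformative. If the global covariates are kept (region drops out within one region), treatment, co-morbid asthma/AERD/NSAID-ERD status and prior surgery status are three parameters resting on that handful of events. Japanese counts are further reduced by the site exclusions in SAP 2.1.4.

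**Working it through.** The limits are stipulated, so there is no derived figure to reproduce. The check is to list what the rule does, and then to see how often it matters at the plan's own event rates.

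**What the rule does.** Let a and b be the events in the two arms.

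- As written, skip if (a + b < 10) and (a < 2 and b < 2).
- If a ≤ 1 and b ≤ 1, then a + b ≤ 2 < 10, so the first condition is always met when the second is. The rule equals the second condition alone.
- The skipped pairs are (0,0), (0,1), (1,0) and (1,1).
- The number of pairs with a + b ≤ 9 is 1 + 2 + … + 10 = 55, so 55 − 4 = 51 pairs below 10 events are still fitted. The smallest fitted total is 2, at 2 v 0.

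| Rule | Pairs below 10 events still fitted | Smallest total fitted | Empty arm fitted? |
|---|---|---|---|
| As written | 51 of 55 | 2 | yes, from 2 v 0 |
| 'and' kept, 'each' read as 'either' | 21 of 55 | 4 (2 v 2) | yes, from 10 v 0 |
| 'or', 'each' kept as both arms | 0 of 55 | 10 | yes, from 10 v 0 |
| 'or' with 'either' | 0 of 55 | 10 | no |

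**Precision when a fit is possible.** With SE(log HR) ≈ √(1/a + 1/b), the 95% interval is the hazard ratio divided and multiplied by exp(1.96 × SE). For 2 v 1 events, SE = √1.5 = 1.22 and the factor is 11.0. For 2 v 2, SE = 1 and the factor is 7.1.

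**How often it matters.** Inputs from SAP 1.3 are HR 0.33 with a placebo Week 52 rate of 11% for surgery decision and 35% for the composite. The active rate is 1 − (1 − p)^0.33:

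- Surgery decision: 1 − 0.89^0.33 = 0.0377.
- Composite: 1 − 0.65^0.33 = 0.1325.

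As a check on these inputs, 200 per arm gives 200 × (0.11 + 0.0377) = 29.5 surgery-decision events. Schoenfeld power is then 85.4% at the 5% level, consistent with the stated minimum of 80%. The planning figures are not in question.

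Regional arm sizes are assumed to be 15, 20, 30 or 40. Events are treated as independent binomials. One case in full, for surgery decision at 20 per arm:

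- P(0 or 1 placebo event) = 0.0972 + 0.2403 = 0.3375
- P(0 or 1 active event) = 0.4634 + 0.3634 = 0.8268
- P(skipped) = 0.3375 × 0.8268 = 0.279, so P(fitted) = 0.721

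All cases, as percentages:

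| | 15 per arm | 20 | 30 | 40 |
|---|---|---|---|---|
| **Surgery decision** | | | | |
| Fitted, rule as written | 56 | 72 | 90 | 97 |
| Fitted with <10 events | 56 | 72 | 89 | 90 |
| Fitted with an empty arm | 30 | 32 | 28 | 21 |
| Skipped under 'or' with 'either' | >99 | >99 | 99 | 94 |
| **Composite** | | | | |
| Fitted with <10 events | 84 | 49 | 6 | 0.2 |
| Fitted with an empty arm | 12 | 6 | 1.4 | 0.3 |
| Skipped under 'or' with 'either' | 85 | 54 | 11 | 3 |

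The documents give no planning rate for SCS alone, so that endpoint is not computed.

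**The case against.** The strongest reply is that this is a drafting slip in a descriptive section. SAP 4.2.14 does not commit to a Cox model for every endpoint in each country: efficacy is listed among analyses that may be included, and details may be set out elsewhere. Nothing is tested. An undefined hazard ratio would be obvious beside the event counts and curves. This all stands and limits the weight of the point, but it does not make the rule work. An optional separate document does not correct a rule stated here.

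A second reply is that 'each' may have been meant as 'either'. The 10-event limit would then do some work, but the rule would still fit 2 v 2 and 10 v 0.

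A third is that surgery decision is the less favourable of the two endpoints with planning rates. That is right. At 30 to 40 per arm the composite is hardly affected, so the surgery-decision percentages should not be read as general.

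A reader might also infer that the trial's confirmatory results or type I error are at risk. The documents do not support this: the restriction sits only in the regional section, and the global Cox analyses and testing hierarchy do not use it. Nor do they state the intended rule. That 'or' with 'either' was meant is an inference from a 10-event limit that otherwise has no function.

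**Conclusion.** The point holds. That the 10-event limit is inoperative follows from the sentence and the two-arm design, with no assumption about event rates. As written, the rule blocks only four pairs of event counts and permits fits on 2 events or with an empty arm.

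The practical size depends on regional numbers that the documents do not give. At an assumed 15 to 40 per arm and the planning rates, it is substantial for surgery decision. For the composite it ranges from substantial at 15 per arm to negligible at 40. The consequence is limited to regional estimates presented without p-values. The correction is nearly free and worth making.

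**What to change.** Replace the restriction in SAP 4.2.14 with: *Cox regression is omitted when there are fewer than 10 events in total or fewer than 2 events in either treatment group; event counts and Kaplan-Meier proportions are shown instead.* Both changes are needed, because 'or' alone, with 'each' still meaning both arms, would fit 10 v 0. The Kaplan-Meier estimates are already specified for these endpoints in SAP 3.3.3 and 4.2.7.1.4, so little new programming is involved. If the sponsor does want Cox fitted on 2 events, the 10-event limit should be deleted and that choice stated.

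The cost is a short edit, with no effect on data collection or the global analyses. Fewer regional hazard ratios would be shown: at the assumed sizes, surgery decision would be skipped in at least 94% of cases, and the composite in 85% at 15 per arm but 3% at 40.
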